6.5.3. Rescue Medicine

There is no rescue therapy to reverse the adverse events (AEs) observed with PF-06865571; standard medical supportive care must be provided to manage the AEs.

6.6. Dose Modification

By design, this study only includes administration of a single, oral dose of PF-06865571. As such, dose modifications will not be made during the study.

6.7. Intervention After the End of the Study

No intervention will be provided to study participants at the end of the study.

7. DISCONTINUATION OF STUDY INTERVENTION AND PARTICIPANT DISCONTINUATION/WITHDRAWAL

7.1. Discontinuation of Study Intervention

In rare instances, it may be necessary for a participant who was dosed on Day 1 to permanently discontinue from the study. In such circumstances, procedures outlined under early termination visit in the [Schedule of Activities](#) Table must be attempted.

See the [SoA](#) for data to be collected at the time of intervention discontinuation and follow-up and for any further evaluations that need to be completed.

7.2. Participant Discontinuation/Withdrawal From the Study

A participant may withdraw from the study at any time at his/her own request, or may be withdrawn at any time at the discretion of the investigator for safety, behavioral, compliance, or administrative reasons.

At the time of discontinuing from the study, if possible, an early discontinuation visit should be conducted. See the [SoA](#) for assessments to be collected at the time of study discontinuation and follow-up and for any further evaluations that need to be completed.

The early discontinuation visit applies only to participants who are randomized and then are prematurely withdrawn from the study. Participants should be questioned regarding their reason for withdrawal. The participant will be permanently discontinued both from the study intervention and from the study at that time.

If a participant withdraws from the study, he/she may request destruction of any remaining samples, but data already generated from the samples will continue to be available, and may be used to protect the integrity of existing analyses. The investigator must document any such requests in the site study records.

If the participant withdraws from the study and also withdraws consent (see below) for disclosure of future information, no further evaluations should be performed and no additional data should be collected. The sponsor may retain and continue to use any data collected before such withdrawal of consent.

When a participant withdraws from the study because of a serious adverse event (SAE), the SAE must be recorded on the case report form (CRF) and reported on the Clinical Trial (CT) SAE Report.

Lack of completion of all or any of the withdrawal/early termination procedures will not be viewed as protocol deviations so long as the participant's safety was preserved.

Withdrawal of Consent:

Participants who request to discontinue receipt of study treatment will remain in the study and must continue to be followed for protocol-specified follow-up procedures. The only exception to this is when a participant specifically withdraws consent for any further contact with him or her or persons previously authorized by the participant to provide this information. Participants should notify the investigator in writing of the decision to withdraw consent from future follow-up, whenever possible. The withdrawal of consent should be explained in detail in the medical records by the investigator, as to whether the withdrawal is only from further receipt of investigational product or also from study procedures and/or posttreatment study follow-up, and entered on the appropriate CRF page. In the event that vital status (whether the participant is alive or dead) is being measured,

publicly available information should be used to determine vital status only as appropriately directed in accordance with local law.

7.3. Lost to Follow up

A participant will be considered lost to follow-up if he or she repeatedly fails to return for scheduled visits and is unable to be contacted by the study site.

The following actions must be taken if a participant fails to return to the clinic for a required study visit:

- The site must attempt to contact the participant and reschedule the missed visit as soon as possible and counsel the participant on the importance of maintaining the assigned visit schedule and ascertain whether or not the participant wishes to and/or should continue in the study;
- Before a participant is deemed lost to follow-up, the investigator or designee must make every effort to regain contact with the participant (where possible, 3 telephone calls and, if necessary, a certified letter to the participant's last known mailing address or local equivalent methods). These contact attempts should be documented in the participant's medical record;
- Should the participant continue to be unreachable, he/she will be considered to have withdrawn from the study.

Discontinuation of specific sites or of the study as a whole is handled as part of [Appendix 1](#).

8. STUDY ASSESSMENTS AND PROCEDURES

Participants will be screened within 28 days prior to administration of the investigational product to confirm that they meet the study population criteria for the study. The investigator (or an appropriate delegate at the investigator site) must obtain a signed and dated ICD before performing any study-specific procedures. If the time between screening and dosing exceeds 28 days as a result of unexpected delays (eg, delayed drug shipment), then participants do not require rescreening if the laboratory results obtained prior to first dose administration meet eligibility criteria.

A participant who qualified for this protocol but did not enroll from an earlier cohort/group may be used in a subsequent cohort/group without rescreening, provided laboratory results obtained prior to the first dose administration meet eligibility criteria for this study. C
Cl

Study procedures and their timing are summarized in the [SoA](#). Protocol waivers or exemptions are not allowed.

Immediate safety concerns should be discussed with the sponsor immediately upon occurrence or awareness to determine if the participant should continue or discontinue study intervention.

Adherence to the study design requirements, including those specified in the [SoA](#), is essential and required for study conduct.

All screening evaluations must be completed and reviewed to confirm that potential participants meet all eligibility criteria. The investigator will maintain a screening log to record details of all participants screened and to confirm eligibility or record reasons for screening failure, as applicable.

Every effort should be made to ensure that protocol-required tests and procedures are completed as described. However, it is anticipated that from time to time there may be circumstances outside the control of the investigator that may make it unfeasible to perform the test. In these cases, the investigator must take all steps necessary to ensure the safety and well-being of the participant. When a protocol-required test cannot be performed, the investigator will document the reason for the missed test and any corrective and preventive actions that he or she has taken to ensure that required processes are adhered to as soon as possible. The study team must be informed of these incidents in a timely manner.

If an intravenous (IV) catheter is utilized for blood sample collections, ECGs and vital sign assessments (pulse rate and BP) should be collected prior to the insertion of the catheter.

For samples being collected and shipped, detailed collection, processing, storage, and shipment instructions and contact information will be provided to the investigator site prior to initiation of the study.

The total blood sampling volume for individual participants in this study is approximately 175 mL. The actual collection times of blood sampling may change. Additional blood samples may be taken for safety assessments at times specified by Pfizer, provided the total volume taken during the study does not exceed 300 mL during any period of 60 consecutive days.

To prepare for study participation, participants will be instructed on the information in the [Lifestyle Considerations](#) and [Concomitant Therapy](#) sections of the protocol.

8.1. Efficacy Assessments

Analysis of efficacy is not applicable to this study.

8.2. Safety Assessments

Planned time points for all safety assessments are provided in the [SoA](#). Unscheduled clinical laboratory measurements may be obtained at any time during the study to assess any perceived safety concerns.

8.2.1. Physical Examinations

Physical examinations may be conducted by a physician, trained physician's assistant, or nurse practitioner as acceptable according to local regulation as defined in the [Schedule of Activities](#).

- A **full physical examination** will include head, ears, eyes, nose, mouth, skin, heart and lung examinations, lymph nodes, gastrointestinal, musculoskeletal, and neurological systems.
- A **limited physical examination** will be focused on general appearance, the respiratory, cardiovascular, and neurological systems, as well as towards participant reported symptoms, performed at Investigator discretion.

For measuring body weight, a scale with appropriate range and resolution is used and must be placed on a stable, flat surface. Participants must remove shoes, bulky layers of clothing, and jackets so that only light clothing remains. They must also remove the contents of their pockets and remain still during measurement of weight.

8.2.2. Vital Signs

Blood pressure and pulse rate will be measured as defined in the [Schedule of Activities](#). Additional collection times, or changes to collection times of blood pressure and pulse rate will be permitted, as necessary, to ensure appropriate collection of safety data.

- **Single, seated** blood pressure/pulse rate will be measured with the participant's arm supported at the level of the heart, and recorded to the nearest mmHg, following a rest of **≥5 minutes**;
- Same arm (preferably the dominant arm) will be used for blood pressure/pulse rate assessment throughout the study;
- Blood pressure/pulse rate assessment should **not** be taken from the arm with an intravenous catheter, if placed;
- Participants should be instructed **not** to speak during blood pressure/pulse rate measurements.

The same properly sized and calibrated BP cuff will be used to measure BP each time. The use of an automated device for measuring BP and pulse rate is acceptable; however, when done manually, pulse rate will be measured in the brachial/radial artery for at least 30 seconds. When the timing of these measurements coincides with a blood collection, BP and pulse rate should be obtained prior to the nominal time of the blood collection.

Additional collection times, or changes to collection times, of BP and pulse rate will be permitted, as necessary, to ensure appropriate collection of safety data.

8.2.3. Electrocardiograms

Supine 12-lead ECGs should be collected at times specified in the [SoA](#) section of this protocol using an ECG machine that automatically calculates the heart rate and measures PR, QT, and QTcF intervals and QRS complex. All scheduled ECGs should be performed after the participant has rested quietly for at least 10 minutes in a supine position.

To ensure safety of the participants, a qualified individual at the investigator site will make comparisons to baseline measurements. Additional ECG monitoring will occur if a) a postdose QTcF interval is increased by ≥ 30 msec from the baseline **and** is >450 msec; or b) an absolute QTcF value is ≥ 500 msec for any scheduled ECG. If either of these conditions occurs, then 2 additional ECGs will be collected approximately 2 to 4 minutes apart to confirm the original measurement. If the QTcF values from these repeated ECGs remain above the threshold value, then a single ECG must be repeated at least hourly until QTcF values from 2 successive ECGs fall below the threshold value that triggered the repeat measurement.

If a postdose QTcF interval remains ≥ 30 msec from the baseline **and** is >450 msec; or b) an absolute QTcF value is ≥ 500 msec for any scheduled ECG for greater than 4 hours (or sooner, at the discretion of the investigator), or QTcF intervals get progressively longer, the participant should undergo continuous ECG monitoring. A cardiologist should be consulted if QTcF intervals do not return to less than the criterion listed above after 8 hours of monitoring (or sooner, at the discretion of the investigator).

In some cases, it may be appropriate to repeat abnormal ECGs to rule out improper lead placement as contributing to the ECG abnormality. It is important that leads be placed in the same positions each time in order to achieve precise ECG recordings. If a machine-read QTcF value is prolonged, as defined above, repeat measurements may not be necessary if a qualified medical provider's interpretation determines that the QTcF values are in the acceptable range.

ECG values of potential clinical concern are listed in [Appendix 7](#).

8.2.4. Clinical Safety Laboratory Assessments

See [Appendix 2](#) for the list of clinical safety laboratory tests to be performed and the [SoA](#) for the timing and frequency.

The investigator must review the laboratory report, document this review, and record any clinically relevant changes occurring during the study in the AE section of the CRF. Clinically significant abnormal laboratory findings are those which are not associated with the underlying disease, unless judged by the investigator to be more severe than expected for the participant's condition.

All laboratory tests with values considered clinically significantly abnormal during participation in the study or within 5 days after the last dose of study intervention should be repeated until the values return to normal or baseline or are no longer considered clinically significant by the investigator or medical monitor.

If such values do not return to normal/baseline within a period of time judged reasonable by the investigator, the etiology should be identified and the sponsor notified.

All protocol-required laboratory assessments, as defined in [Appendix 2](#), must be conducted in accordance with the laboratory manual and the [SoA](#).

If laboratory values from non-protocol-specified laboratory assessments performed at the institution's local laboratory require a change in participant management or are considered clinically significant by the investigator (eg, SAE or AE or dose modification), then the results must be recorded in the CRF.

8.2.5. Pregnancy Testing

Pregnancy tests may be urine or serum tests, but must have a sensitivity of at least 25 mIU/mL. Urine pregnancy tests will be performed in women of childbearing potential (WOCBP) at the times listed in the [SoA](#), onsite. In addition, blood sample will be analyzed by the sponsor-identified central laboratory, in all females consented in this study. In WOCBP, following a negative pregnancy test result at screening, appropriate contraception must continue *or* be commenced and a second negative pregnancy test result will be required at the baseline visit (ie, urine testing on Day 1) prior to the participant's receiving the investigational product. Pregnancy tests will also be done whenever 1 menstrual cycle is missed during the active treatment period (or when potential pregnancy is otherwise suspected) and at the end of the study. Pregnancy tests may also be repeated if requested by institutional review boards (IRBs)/ethics committees (ECs) or if required by local regulations. On Day 1, if a urine test cannot be confirmed as negative (eg, an ambiguous result), a serum pregnancy test is required with results reported by the sponsor-identified central laboratory; and in this case, dosing with PF-06865571 must be delayed. The participant must be excluded if the serum pregnancy result is positive.

8.3. Adverse Events and Serious Adverse Events

The definitions of an AE and an SAE can be found in [Appendix 3](#).

AEs will be reported by the participant (or, when appropriate, by a caregiver, surrogate, or the participant's legally authorized representative).

The investigator and any qualified designees are responsible for detecting, documenting, and recording events that meet the definition of an AE or SAE and remain responsible to pursue and obtain adequate information both to determine the outcome and to assess whether it meets the criteria for classification as an SAE or that caused the participant to discontinue the study (see [Section 7](#)).

In addition, the investigator may be requested by Pfizer Safety to obtain specific follow-up information in an expedited fashion.

8.3.1. Time Period and Frequency for Collecting AE and SAE Information

The time period for actively eliciting and collecting AEs and SAEs (“active collection period”) for each participant begins from the time the participant provides informed consent, which is obtained before the participant’s participation in the study (ie, before undergoing any study-related procedure and/or receiving investigational product), through and including a ***minimum of 28 calendar days*** after the last administration of the investigational product.

For participants who are screen failures, the active collection period ends when screen failure status is determined.

Medical occurrences that begin before the start of study intervention but after obtaining informed consent will be recorded on the Medical History/Current Medical Conditions section of the case report form (CRF), not the AE section.

Follow-up by the investigator continues throughout and after the active collection period and until the event or its sequelae resolve or stabilize at a level acceptable to the investigator, and Pfizer concurs with that assessment.

Investigators are not obligated to actively seek AEs or SAEs after conclusion of the study participation. However, if the investigator learns of any SAE, including a death, at any time after a participant has been discharged from the study, and he/she considers the event to be reasonably related to the study intervention or study participation, the investigator must promptly notify the sponsor.

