1.2. Schema

1.3. Schedule of Activities (SoA)

The table provides an overview of the protocol visits and procedures. Refer to [STUDY ASSESSMENTS AND PROCEDURES](#) section of the protocol for detailed information on each procedure and assessment required for compliance with the protocol. The investigator may schedule visits (unplanned visits) in addition to those listed in the SoA table, in order to conduct evaluations or assessments required to protect the well-being of the participant.

Visit Identifier/Day [for list of abbreviations refer to Section 10.9]	Screen ≤-28 to -2	Day -1	Day 1													Day 2		Day 3 ^a	Day 4 ^a	ET	Follow-Up
			0	0.5	1	2	4	6	7	8	10	12	14	16	24	36	48	72	Day 30±2		
Hours Post Dose		--	0	0.5	1	2	4	6	7	8	10	12	14	16	24	36	48	72	--	--	
Informed consent & demography	X																				
Outpatient visit	X																	X ^a	X		
Inpatient stay at Clinical Research Unit		X	→	→	→	→	→	→	→	→	→	→	→	→	→	→	X ^a	X ^a			
Eligibility assessment	X	X																			
Medical history	X	X																			
Physical exam (height & body weight at Screen, only) ^b	X	X															X ^c	X ^c	X		
Breath alcohol test	X	X																			
Alcohol/tobacco & contraception use	X	X																X ^{c,d}	X	X ^e	
(Update) prior/concomitant treatments	X	X																X ^{c,d}	X	X	
Single, supine 12-lead ECG	X		X														X ^c	X ^c	X		
Single, seated vital sign assessment (BP and pulse rate)	X		X														X ^c	X ^c	X		
Serious and non-serious adverse event monitoring	X	X	→	→	→	→	→	→	→	→	→	→	→	→	→	→	X ^c	X ^c	X	X	
Standard meals ^f		X	X			X		X		X		X		X		X	X	X ^c			
Investigational product administration			X ^g																		
Blood for clinical laboratory tests after ≥4-hour fast	X		X														X ^c	X ^c	X		
Blood FSH (females only), HIV, HBsAg, HCVAb/RNA	X																				
Blood for pregnancy test (females only)	X		X														X ^c	X ^c	X		
CCI																					
Blood for pharmacokinetic sampling for PF-06865571			X	X	X	X	X	X		X	X	X		X	X	X	X	X ^c	X		
Urine drug test		X																			
Urinalysis (and microscopy, if needed)	X		X														X ^c	X ^c	X		
Urine pregnancy test (WOCBP, only)			X																		

- Participants discharged post completion of procedures (Cohort 1, *only*); in Cohorts 2-4, discharge (with subsequent outpatient visit) permitted *or* stay can continue to Day 4.

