- Full physical (PE) exam at Screen; at all other time points, limited PE for findings during previous PE or new/open AEs *only*, at Investigator discretion.
- On Day 3**, procedures limited to Cohort 1, *only*; **on Day 4**, procedures limited to Cohorts 2-4, *only*.
- In Cohorts 2-4 *only*, procedures to be completed *only if* participant is discharged on Day 3 and returns for outpatient visit on Day 4.
- Confirmation of appropriate contraception use *only*.
- Meals/snacks to be served at clock times matching approximately 0H, 4H, 7H, 10H, and 14H (optional) relative to dosing on Day 1 (while inpatient).
- Dosing to occur with standard morning meal provided approximately 30 minutes prior to 0H, and completed approximately 10 minutes prior to dosing.

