4.4. End of Study Definition

A participant is considered to have completed the study if he/she has completed all phases of the study including the follow-up visit via telephone contact shown in the [schedule of activities](#).

The end of the study is defined as the date of the follow-up visit via telephone contact, shown in the [schedule of activities](#), for the last participant in the trial globally.

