10.4. Appendix 4: Contraceptive Guidance and Collection of Pregnancy Information

10.4.1. Male Participant Reproductive Inclusion Criteria

Male participants are eligible to participate if they agree to the following requirements during the intervention period and for at least 28 days after the last dose of study intervention, which corresponds to the time needed to eliminate study intervention(s):

- Refrain from donating sperm.

PLUS either:

- Be abstinent from heterosexual intercourse with a female of childbearing potential as their preferred and usual lifestyle (abstinent on a long-term and persistent basis) and agree to remain abstinent.

OR

- Must agree to use a male condom when engaging in any activity that allows for passage of ejaculate to another person.
- In addition to male condom use, a highly effective method of contraception may be considered in WOCBP partners of male participants (refer to the list of highly effective methods below in [Section 10.4.4](#)).

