6.2. Safety Endpoints

The following data are considered in standard safety summaries (see protocol for collection days and list of parameters):

- adverse events,
- laboratory data,
- vital signs data,
- ECG results.

All events that start on or after the first dosing day and time and during the active collection period as specified in the protocol will be counted as treatment emergent adverse event (TEAE). Events that occur in a non-treatment period (for example, Follow-up) will be counted as treatment emergent and attributed to the treatment taken. For the safety endpoints Day 1 planned predose measurements will serve as baseline.

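### The SoA follow-up window opens on Day 28, 27 days after the dose and one day short of the 28-day minimum for active AE/SAE collection in Protocol 8.3.1

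*Protocol*

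**What the plan says.** Protocol 8.3.1 starts active collection of AEs and SAEs at informed consent and continues it through and including a "minimum of 28 calendar days" "after the last administration of the investigational product". Protocol 6.6 confirms that there is one administration: "By design, this study only includes administration of a single, oral dose of PF-06865571". The SoA (Protocol 1.3) places that dose on Day 1 at hour 0.

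In the SoA row "Serious and non-serious adverse event monitoring", the last marked column is Follow-Up, at Day 30±2. No assessment is scheduled after it. Protocol 4.4 treats that telephone call as the end of the participant's study: "A participant is considered to have completed the study if he/she has completed all phases of the study including the follow-up visit via telephone contact". Protocol 8.3.1 adds that investigators need not actively look for events once participation has concluded.

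Two linked provisions use the same timing. Protocol 10.4.1 asks male participants to meet the reproductive requirements "for at least 28 days after the last dose of study intervention", and 10.4.2 sets the same period for women of childbearing potential. The SoA has contraceptive use confirmed at the follow-up contact. SAP 6.2 says that events starting on or after dosing and "during the active collection period as specified in the protocol will be counted as treatment emergent adverse event (TEAE").

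**The concern.** Protocol 8.3.1 states a minimum, and the SoA is what sites schedule from; Protocol 8 calls adherence to it essential and required. If the SoA window includes a day that does not reach the minimum, a site can follow the SoA exactly and still fall short of 8.3.1, with no later visit to make up the difference.

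What is at stake is one day of actively elicited safety follow-up, in a study whose secondary objective is safety and tolerability, and an avoidable source of protocol deviations. Nothing in the PK analysis depends on it.

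**Working it through.** **Inputs**

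- Dose: single, Day 1, hour 0 (Protocol 1.3 and 6.6).
- Follow-up contact: Day 30±2, that is Day 28 to Day 32 (Protocol 1.3).
- Minimum active collection: 28 calendar days after the last administration (Protocol 8.3.1).
- Screening: Day -28 to Day -2 (Protocol 1.3).
- Stated participation: 5 to 9 weeks (Protocol 4.1).

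**Day numbering.** The SoA labels 24 h as Day 2, 48 h as Day 3 and 72 h as Day 4. It goes from Day -1 to Day 1, with no Day 0. Hence days after dose = study day - 1.

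**The plan's own figure.** The stated participation range is the only figure in the documents that depends on the follow-up day. With no Day 0, the number of study days from Screening Day -a to contact Day b is a + b.

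- Shortest: Day -2 to Day 28 = 2 + 28 = 30 days; 30/7 = 4.29 weeks, which rounds up to 5.
- Longest: Day -28 to Day 32 = 28 + 32 = 60 days; 60/7 = 8.57 weeks, which rounds up to 9.

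Both stated ends are reproduced after rounding up to whole weeks, so the day numbering is consistent. The figure does not show whether Day 28 was meant to be excluded: a shortest span ending on Day 30 (32/7 = 4.57) or Day 32 (34/7 = 4.86) also rounds up to 5.

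**Check against the minimum**

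| Contact on | Days after dose | At least 28? |
|---|---|---|
| Day 28 | 28 - 1 = 27 | No, short by 1 |
| Day 29 | 29 - 1 = 28 | Yes |
| Day 30 (nominal) | 30 - 1 = 29 | Yes |
| Day 31 | 31 - 1 = 30 | Yes |
| Day 32 | 32 - 1 = 31 | Yes |

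One of the five permitted days falls short. Day 28 would pass only if the dosing day were itself counted as the first of the 28, which does not fit a period defined as running after the administration.

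**Does the call stop active collection?** No sentence says so. It follows from three things together: follow-up is the last AE-monitoring entry in the SoA, the call completes participation (4.4), and active seeking is not required after participation concludes (8.3.1).

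**The case against.** The strongest reply is that this is a loose window and not a contradiction. A site satisfies both provisions by calling on any of Days 29 to 32, and the visit is targeted at Day 30. Section 8.3.1 can be read as governing, so that a site calling on Day 28 still owes collection through Day 29, and the SoA introduction allows unplanned visits. SAEs that come to the investigator's attention later remain reportable (8.3.1.1). The day in question is also about four weeks after a single dose of a drug that the protocol describes as having a relatively short half-life.

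Most of that stands, and it limits the point to a minor one. It does not remove it: no text tells a site to avoid Day 28, says that 8.3.1 overrides the SoA window, or requires the extra contact that a Day 28 call would make necessary.

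A reader might infer more than the documents support in four respects:

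- **That the contraception minimum is broken as well.** The requirement in 10.4 is the participant's undertaking, and the call does not release anyone from it. Only the confirmation can come a day early.
- **That the TEAE window shrinks.** SAP 6.2 ties TEAEs to the period specified in the protocol, not to the contact date, and it counts events during follow-up as treatment emergent. What could be lost is elicitation on one day, not eligibility to be counted.
- **That collection would differ between cohorts.** The window is the same for all four, and nothing in the documents points to a systematic difference.
- **That about a fifth of participants are affected.** An even spread of calls over five days would give 24/5 = 4.8 of about 24, but the documents give no distribution of contact days. The range is 0 to all participants, and it is 0 if sites call on or after the nominal day.

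**Conclusion.** The point holds in a narrow form. The SoA permits the last scheduled AE contact on Day 28, 27 days after dosing, one day less than Protocol 8.3.1 requires. The other four days of the window comply.

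The day count rests only on the SoA's own numbering and on reading the 28 days as excluding the dosing day. That active elicitation would then stop a day early is an inference from 4.4, from 8.3.1 and from the absence of a later contact; an unplanned contact would prevent it. The consequence is at most one day of active elicitation per participant called on Day 28, for an unknown number of participants. The primary PK endpoints, the sample size and the ANOVA are untouched. It is a minor inconsistency, worth correcting because the correction is so small.

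**What to change.** Reconcile the SoA with Protocol 8.3.1 in one of two ways:

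1. Change the Follow-Up cell so that no in-window contact falls before Day 29. For example, Day 30 -1/+2 gives Days 29 to 32, or 28 to 31 days after dosing. The contraception confirmation then also falls no earlier than 28 days after the dose. The cost is one SoA cell and one day less flexibility for the telephone call.
2. Keep Day 30±2 and state that active AE/SAE collection runs through Day 29 whatever the contact date, with a defined means of collecting it, such as a second call for anyone contacted on Day 28. This keeps the full window but adds a possible extra contact.

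The first is simpler. Neither needs a change to the SAP, and the stated participation range of 5 to 9 weeks still holds: under the first option the shortest span is 2 + 29 = 31 days (31/7 = 4.43 weeks, rounding up to 5) and the longest remains 60 days.
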